2.5.4 Multiplex Immunofluorescence (mIF)

Immunohistochemistry is one of the most acceptable tools to measure PD-1 and PD-L1 expression in tumor microenvironment (TME). Human BM core biopsy will be decalcified for immunohistochemistry (IHC). We will compare IHC/IF findings and its quantitative analyses by using Multiplex Immunofluorescence (mIF) (will be describe below) with flow cytometric data in BM aspirate and blood. All these procedures will be performed with a collaboration with [name] [name] at MDACC CIMAC. For multiplex IF image analysis platform, we will use the tyramide signal amplification (TSA) methodology through the Opal™ workflow and chemistry which allows simultaneous staining of multiple biomarkers within a single paraffin tissue section. The multispectral microscopy Vectra™ and Vectra-Polaris™ scanner systems

(Akoya Biosciences, Waltham, MA, USA) including the image analysis software (InForm, Akoya Biosciences) allows the analysis of the multispectral images generated by this staining methodology. Multiplex ImmunoFluorescence (IF) staining will be performed on FFPE tumor slides using the following panels and antibodies:

1. **Panel 1 (PD-L1/PD-1 and TIL Panel):** PD-L1, CD68, PD-1, CD8, CD3, PanCytokeratin, DAPI.
2. **Panel 2 (T cell Activation/ Regulatory Panel):** FOXP3, Granzyme B, CD45RO, CD8, CD3, PanCytokeratin, DAPI.

2.5.5 Dynamic change of immune cell subsets:

We will possibly have limited number of cells in the BM aspirate. Therefore, we will analyze the immune profile combining a high-throughput technique that will allow us to study more than 20 markers in a single cell analysis using CyTOF. These techniques will provide information about the architecture of TME (*i.e.* BM) and the distribution of markers of interest detected with CyTOF. CyTOF-based single cell analysis is a new technology that combines flow cytometry with metal-conjugated antibodies detected by mass spectrometry permitting higher order multiplexing (up to 100 molecules) on a single cell analysis (Bendall *et al.*, 2011). Additionally, after fixation and permeabilization, cells will be stained with anti-human Ki-67-151Eu (B56;BD Pharmingen Ab conjugated with lanthanide MaxPar Europium Chloride 151Eu using the MaxPar X8 Ab labeling kit) for 30 min at room temperature. Cells will be acquired on CyTOF 2 instrument (DVS; Fluidigm Sciences). All data will be analyzed, and graphs generated using the DVS Cytobank software (Cytobank).

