While measurable residual disease (MRD) is a well-recognized predictive biomarker for relapse in AML, the current standard of care MRD detection technique – namely multi-parameter flow cytometry (MFC) – does not accurately predict leukemic relapse, due to poor reproducibility and sensitivity, thereby limiting the utility of MFC-based MRD as a reliable surrogate end-point in AML clinical trials. With the growing, unmet need for more accurate MRD approaches in AML studies, the current application seeks to leverage the unprecedented accuracy and sensitivity of the sophisticated duplex sequencing technology to capture very low-level circulating tumor DNA (ctDNA), also known as circulating tumor free DNA (ctfDNA). As a strategy to potentially more accurately predict early relapse. The proposed DS-based ctDNA MRD detection approach will not only serve as a proof-of-principle study supporting its utility as a powerful biomarker of relapse in AML but, if shown to be a more accurate predictor of relapse, will lay grounds for its implementation as a potential surrogate marker of long-term response in future AML clinical trials.

For this assay, samples of 8mL will be collected at each time point in which MRD is collected from peripheral blood. This collection will be in Streck tubes that are provided to sites. Aside from the different type of tube. These sample will be collected, processed and shipped in the same manner and with the MRD tubes at the different time points. These samples will be sent to [name] laboratory where they will be stored, and subsequently sent to [name] laboratory where the assays will be conducted.

2.5.3 Assessment of immune cell subsets and its correlation with the response to combine chemotherapy and anti-PD-1 directed therapy

Currently, there is no single biomarker to predict the response to anti-PD-1 Ab therapy especially in myeloid leukemia. Two recent landmark studies suggest that the predicted response of anti-PD-1 is associated with PD-L1 expression in tumor-infiltrating immune cells (Herbst *et al.*, 2014; Powles *et al.*, 2014). These studies have led us to test the question about the expression of PD-L1 on blasts from human AML BM and blood and its correlation with the response to combined anti-PD-1/chemotherapy in AML.

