5.8 Biomarker Plan

List of Biomarker Assays in Order of Priority

Note for participating sites: Please see Section 5.1 for details on specimens to collect. The specimens tested are not always the same specimens that are submitted by the site, as processing of blood and tissue will occur at the Biobank prior to testing.

Priority	Biomarker Name	Assay (CLIA: Y/N)	Use in the Trial and Purpose	Specimens Tested	Collection Time Points	Mandatory or Optional	Assay Laboratory and Lab PI
Core Biopsy Biomarkers							
1	Multiplex Immunofluorescence	MultiplexIF CLIA: N	Exploratory Correlate with clinical response	FFPE Bone Marrow Core Biopsy, decalcified	Baseline, end of consolidation, after 6 months of treatment, after 1 year of treatment, and at relapse	M/O (optional for the after 6 months of treatment and after 1 year of treatment time points)	CIMAC [name] [contact] [name] [contact] [name] [contact]
Bone Marrow Aspiration Biomarkers							
1	CBF gene alterations	Cytogenetics or Fluorescence In situ Hybridization (FISH) testing CLIA: Y	Integral Stratification factor	Bone marrow aspirate	Baseline and as clinically indicated	M	Local CLIA labs
2	FLT3 Mutations	Molecular FLT3 assay (either FLT3 -PCR testing or as a part of Next generation sequencing panel) CLIA: Y	Integral Exclusion factor	N/A (collected as part of the CBF gene alterations assay)	Baseline and as clinically indicated	M	Local CLIA labs

Priority	Biomarker Name	Assay (CLIA: Y/N)	Use in the Trial and Purpose	Specimens Tested	Collection Time Points	Mandatory or Optional	Assay Laboratory and Lab PI
5	Immune cell subset Analysis (CyTOF)	CyTOF CLIA: N	Exploratory Correlate with clinical responses	Mononuclear cells from Bone marrow aspirate in EDTA	Baseline, end of consolidation, after 6 months of treatment, after 1 year of treatment, and at relapse	M/O (optional for the after 6 months of treatment and after 1 year of treatment time points)	MDACC CIMAC [name] [name] [contact] [name] [contact] [name] [contact]
6	Olink	Olink CLIA: N	Exploratory Correlate with clinical responses	Plasma from Bone marrow aspirate in EDTA	Baseline, end of consolidation, after 6 months of treatment, after 1 year of treatment, and at relapse	M/O (optional for the after 6 months of treatment and after 1 year of treatment time points)	Mt. Sinai CIMAC [name] [contact]

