10.4.2.3 PD-1 and PD-L1 expression

An association of clinical response with the expression of PD-L1 AML BM cells will be assessed by a Pearson Chi-square test on a 2×2 table of frequencies. The dependent variable will be defined as response (yes *vs.* no), and QIF categories (negative *vs.* positive) will be the independent variables. We will also monitor the dynamic change of PD-L1 expression over the course of treatment and its correlation with clinical response. Longitudinal measurements of PD-L1 will be examined using mixed-effects modeling.

We will assess immune cell markers at different time points of therapy: at baseline (prior to application of 7+3 chemotherapy), at the end of consolidation, after 6 months and 1 year of treatment, and at relapse. We also plan to measure CD47 levels on leukemic blasts prior to and after chemotherapy and Pembrolizumab (MK-3475) administration to see whether CD47 expression levels correlate with responders *vs.* non-responders and whether expression levels change at different times of therapy. Statistical analyses of the frequency of CD8⁺, CD4⁺, FoxP3 T_{regs}, CD8⁺/FoxP3⁺ T_{regs}, T_{CM}/T_{EMRA}, T_{EM}/T_{EMRA}, the percentage of Ki67 and GzmB in PD-1⁺, Eomes⁺ CD8 T-cells to compare changes over time from baseline to several time-points will be performed by using mixed effects modeling with a Benjamini-Hochberg correction to control for false discovery rates.

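### The only immunofluorescence panel that carries PD-L1 has no blast marker, so it cannot give the PD-L1 status of AML cells that section 10.4.2.3 sets out to test

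*Combined protocol and SAP*

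**What the plan says.** Section 2.5.3 poses the scientific question as "the expression of PD-L1 on blasts from human AML BM and blood and its correlation with the response" to combined anti-PD-1 and chemotherapy. Section 10.4.2.3 turns it into an analysis: "An association of clinical response with the expression of PD-L1 AML BM cells will be assessed by a Pearson Chi-square test" on a 2×2 table. Response (yes/no) is the dependent variable, "and QIF categories (negative *vs.* positive) will be the independent variables". The same section adds mixed-effects modelling of PD-L1 over the course of treatment. The term QIF is not defined, and no cut-off, cell compartment or sampling time is given for the 2×2 test.

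Section 2.5.4 presents immunohistochemistry and mIF, with quantitative analysis, as the tools for PD-1 and PD-L1 in the marrow microenvironment. Panel 1 is "PD-L1, CD68, PD-1, CD8, CD3, PanCytokeratin, DAPI". Panel 2 is "FOXP3, Granzyme B, CD45RO, CD8, CD3, PanCytokeratin, DAPI" and has no PD-L1. The biomarker table in section 5.8 lists mIF as the only core-biopsy assay. It is run on "FFPE Bone Marrow Core Biopsy, decalcified" and its purpose is correlation with clinical response.

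**The concern.** The analysis needs PD-L1 on leukaemic cells, and the listed panel has no channel that finds them. PanCytokeratin occupies the tumour slot. That it marks epithelial cells is general laboratory knowledge rather than something the protocol states, but the point does not depend on it: no marker that the protocol itself uses to recognise AML cells appears in either panel.

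Two things are at stake. A PD-L1-positive or PD-L1-negative call from Panel 1 could be reported as AML-cell PD-L1 when it is a mixed-cell score. And a change in that score between a leukaemic marrow and a remission marrow could be read as a change in PD-L1 expression when part or all of it is a change in cell mix.

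**Working it through.** **1. Markers set side by side.**

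| Source | Markers |
|---|---|
| mIF Panel 1 (2.5.4) | PD-L1, CD68, PD-1, CD8, CD3, PanCytokeratin, DAPI |
| mIF Panel 2 (2.5.4) | FOXP3, Granzyme B, CD45RO, CD8, CD3, PanCytokeratin, DAPI |
| AML MRD flow tubes (2.5.1.1) | HLA-DR, CD15, CD33, CD19, CD117, CD13, CD38, CD34, CD71, CD45, CD64, CD123, CD4, CD14, CD16, CD56, CD7, CD5 |

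The union of the two mIF rows has no member in common with the flow row.

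**2. What Panel 1 can resolve.** PD-L1 can be placed on CD3/CD8 cells, on CD68-positive cells, on cytokeratin-positive cells, or on cells with none of these labels. Blasts sit in the last group together with normal precursors. Monocytic blasts may instead stain for CD68 and then cannot be told from macrophages. This subgroup matters because the background section on human AML samples reports PD-L1 preferentially in AML-M5.

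**3. Whether the compartment matters.** The same background section reports PD-L1 upregulation of at least 2-fold in 15% of samples for CD34-positive cells, against 32% for peripheral blood mononuclear cells. It also reports that interferon-gamma raised PD-L1 on AML blasts but not in normal controls. On the protocol's own evidence, a mixed-cell score is not a safe stand-in for blast PD-L1.

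**4. Other possible sources.** The flow tubes in 2.5.1.1 contain no PD-L1. The CyTOF descriptions (2.5.5, 10.4.2.2) speak of more than 20 markers but list no PD-L1-plus-blast panel; the marker they plan to measure on blasts is CD47. Neither assay is named as the source of the 10.4.2.3 variable.

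**5. Composition effect (illustration only).** Let *b* be the blast fraction, *p_B* the PD-L1-positive share of blasts and *p_N* that of all other cells. The mixed score is *b·p_B + (1 − b)·p_N*. If neither share changes, its shift is (*b_after − b_before*)(*p_B − p_N*). Entry requires at least 20% blasts, in marrow or blood (3.1.1), and CR requires under 5% in marrow (13.2.2). The blast fractions of 60% and 2% and the PD-L1 shares are assumptions; the documents give no values.

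- *p_B* = 5%, *p_N* = 15%: before, 0.60×0.05 + 0.40×0.15 = 9.0%; after, 0.02×0.05 + 0.98×0.15 = 14.8%. Shift +5.8 points.
- Shares reversed: before, 0.60×0.15 + 0.40×0.05 = 11.0%; after, 0.02×0.15 + 0.98×0.05 = 5.2%. Shift −5.8 points.
- Equal shares: (−0.58)×0 = 0.
- Blasts falling only from 20% to 5%, with shares 10 points apart: 0.15×0.10 = 1.5 points in either direction.

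The sign and size depend on quantities that Panel 1 does not measure, so the shift cannot be corrected afterwards from the same slides.

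**The case against.** The strongest counter-argument is that section 10.4.2.3 never names mIF. QIF is undefined, so tying the variable to Panel 1 is an inference. That stands. The inference is reasonable because no other quantitative immunofluorescence assay is described, but it should be stated as an inference.

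Nor do the documents show that the trial cannot measure blast PD-L1 at all, though a reader might infer it. The question in 2.5.3 covers blood as well as marrow, and mIF uses marrow cores only, so some other assay must supply the blood half. Section 2.5.4 plans a comparison with flow data, and CyTOF runs on marrow and blood. Either might serve; the documents simply list no panel that does so.

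A reader might also infer that the mixed score would correlate with response by construction. It would not. The chi-square test has no stated time point, and a baseline sample precedes any loss of blasts. Patients not in CR/CRi after induction or after consolidation cycle 1 go off study (7.1.1, 7.1.2), so end-of-consolidation cores come almost entirely from responders and offer little responder/non-responder contrast. What remains is confounding of the time trend and a wrong-compartment reading of the chi-square.

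It is likewise tempting to say that in CR at least 95% of the unlabelled cells are normal. The 5% limit applies to marrow blasts overall. If, say, 20% of cells carried a label, 4.9% blasts would be 4.9/80 = 6.1% of the unlabelled cells.

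Finally, Panel 1 is built for PD-1/PD-L1 and infiltrating lymphocytes, and objective 1.3.2 concerns checkpoint expression and immune subsets. The panel can serve that purpose. The mismatch is with the AML-cell question in 2.5.3 and 10.4.2.3.

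**Conclusion.** The mismatch holds. As listed, Panel 1 cannot assign PD-L1 to AML blasts, and no other assay in the documents is specified to do so for the section 10.4.2.3 variable. Following the plan would, on the inference that QIF means the mIF readout, report a mixed-cell score under the name of AML-cell PD-L1. This is more than missing detail, because the listed panel would still return a positive or negative result that looks like an answer.

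No size can be given from the documents. In the assumed scenarios, composition alone moves the score by 0 to 5.8 percentage points in either direction. No reclassification rate follows, because the tested variable is dichotomous and has no stated cut-off.

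The effect is limited to the exploratory PD-L1 time trend and the interpretation of the chi-square test. The primary endpoint, sample size and safety rules are untouched. The point should be fixed, but it does not threaten the trial.

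**What to change.** **Preferred.** Before slides are cut and stained, replace PanCytokeratin in Panel 1 with a blast marker from the trial's flow list (for example CD34, CD117 or CD33) and score PD-L1 on marker-positive cells. No single marker covers all AML, so report how many patients' blasts carry the chosen one. The cost is one antibody change and re-optimisation on decalcified marrow. No new samples are needed: cores are already mandatory at baseline and end of consolidation (5.1), and the biobank cuts slides only on request (6.1.3.1).

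**If the panel cannot change.** State in 10.4.2.3 that the mIF variable is whole-marrow or immune-cell PD-L1, and draw no blast-specific conclusion from it. Use CyTOF for blast PD-L1 only after confirming that its panel includes PD-L1 and a blast gate. This costs a text change and one query to the assay laboratory.

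**In either case.** Define QIF in 10.4.2.3, and name the assay, cell compartment, positivity cut-off and sampling time for the 2×2 test. Report the marrow blast percentage alongside any PD-L1 trend, so that a change in cell mix is visible.

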2.5.6 Olink cytokine panel

Inflammation is a key underlying factor for the pathophysiology of a wide range of diseases, including malignancies. The Olink inflammation biomarker panel provides a high-throughput, multiplex immunoassay enabling analysis of 92 inflammation-related protein biomarkers across 96 samples simultaneously. The objective is to investigate protein signatures associated with response and efficacy. We will perform this procedure on the bone marrow aspirate in collaboration with [name] at Mount Sinai CIMAC.

2.5.7 Whole Exome Sequencing

The determination of the mutation load, a total number of nonsynonymous point mutations, by whole exome sequencing (WES) was shown to be useful in predicting the treatment responses to cancer immunotherapy (Lyu, 2018). Tumor mutational burden (TMB), along with PD-L1 expression, is a useful biomarker for immune checkpoint blockade selection across certain cancer types and TMB determination correlated with WES (Chan, 2019). We will use massively parallel sequencing technology to sequence the genomic DNA of tumor cells (leukemic bone marrow) and normal cells (germline) obtained from patients with AML at baseline. Mutational load by WES will be correlated with clinic-pathological parameters such as response to treatment, survival and immune infiltrating profile, and T cell repertoire diversity and clonality.

2.5.8 RNA-seq

The MD Anderson CIMAC uses Agilent RNA isolation products for RNAseq. RNA will be

prepared using suitable purification system depending on sample source (fresh or FFPE). RNA integrity of FFPE RNA will be assessed using either the Agilent 4200 TapeStation and High Sensitivity RNA ScreenTape or the Agilent 2100 Bioanalyzer and RNA 6000 Pico Chip. Either method will employ the region analysis method to determine the percentage of RNA in the sample that is >200 nt for each sample to be processed. It is necessary to have RNA molecules >200 nt for efficient library construction and this value for each sample will determine appropriate conditions at various steps in the workflow.

2.5.9 TCR-seq

One mechanism by which checkpoint inhibitors are thought to elicit their effects by broadening the TCR repertoire. We will perform high-throughput sequencing of the TCR V β CDR3 regions on flow cytometrically sorted T-cell subsets to assess the effect of immunotherapy on the diversity of the T-cell repertoire and assess for correlation to clinical outcomes. TCR sequencing analysis may be performed using DNA from tumor tissues as well as PBMC. Briefly, 500 ng tumor DNA or 3-6 μ g PBMC DNA will be subjected to high throughput TCR V β CDR3 sequencing on an Illumina HiSeq sequencer with at least 5-fold coverage by ImmunoSEQ™ sequencing (Adaptive Biotechnologies, Seattle, WA). TCR diversity and clonality (defined as $1 - (\text{entropy})/\log_2(\#)$ of productive unique sequences, where the entropy term takes into account the varying clone frequency) will be calculated using a software by Adaptive Technologies. T-cell repertoire diversity and clonality will be correlated with clinic-pathological parameters such as response to treatment, survival, and immune infiltrating profile, as well as genomic profiles (total mutation burden, non-synonymous mutation burden, predicted neoantigen burden, clonal mutation burden and clonal predicted neoantigen burden). TCR profile generated from treatment-refractory tumors at the time of disease progression will be compared to data from pre-treatment tumor samples to explore the TCR repertoire evolution of these tumors under therapeutic pressure. The dynamic changes of TCR from PMBC, when longitudinal blood samples are available, will be correlated to response to immune checkpoint blockade or chemotherapy and survival.

2.5.10 Gut microbiome characterization

There is increasing evidence that dynamic changes within the microbiome can affect both immune and cancer cells. Imbalance in microbial communities promotes chronic inflammation and predisposes to cancer (Garett *et al*, 2015). Our collaborators have shown that microbiome is also involved in the metabolism of drugs and could explain person-to-person variability and responsiveness to therapy (Alexander *et al*, 2017, Zimmermann *et al*, 2019). Unlike in several solid tumors wherein, immune-check point blockade is used alone or in combination or with cytotoxic agents, the drug synergism to treat AML is unique. Majority of these combinations results in mucositis which helps microbes breach gastro-intestinal (GI) epithelial barrier. It is plausible that with each cycle of treatment, exposure of immune cells to time -prevalent oral and GI microbiome is subject to temporal variance. Extrapolating preclinical data, taxonomically unique microbes could further determine priming of antigen presenting cell interaction with immune-effector cells that ultimately determine clinical phenotype. Based on our current understanding on the mechanism of action of PD-1 inhibitors, our overall hypothesis is that gastro-intestinal microbiome holds salutary prognostic and therapeutic promise in patients with AML. Our preliminary hypothesis is that gut microbiome modulate clinical responses and toxicity in patients with AML receiving Check Point Inhibitors (CPI). To this end our proposal will test the longitudinal

relationships between the taxonomy and diversity of gut microbiome on clinical outcomes and toxicity.

3. PATIENT SELECTION

3.1 Eligibility Criteria

3.1.1 Newly diagnosed and pathologically-confirmed AML, confirmed by a bone marrow aspirate and/or biopsy and/or peripheral blood with $\geq 20\%$ myeloid blasts. Bone marrow biopsy, or aspirate or peripheral blood that were obtained up to 3 weeks before signing consent are allowed for purposes of confirming AML diagnosis for eligibility purposes. Secondary AML that is arising from prior myelodysplastic syndrome [MDS] as well as t-AML) are also allowed. Clarifications: . AML arising from myeloproliferative neoplasms (MPN), MPN/MDS overlap (including chronic myelomonocytic leukemia [CMML]) or another myeloid malignancy are NOT allowed. Note 1: Patients must have evidence of bone marrow involvement on aspirate or biopsy. Patients with only extramedullary disease and no bone marrow involvement will be excluded. Note 2 : Every effort should be made to get an aspirate for central flow assessment at screening and all subsequent required time points, but in cases where an aspirate cannot be collected-including dry taps-the patient will not be excluded and assessments will be performed on PB which should be collected at every time that BM is collected. Note 3: Some patients with AML require initiation of therapy quickly after diagnosis, and full metaphase karyotype results in some centers can take 2-3 weeks to result. To avoid this issue being an impediment to accrual to study or to cause delays in initiation of therapy in patients who need fast initiation of therapy, we allow use of karyotype and/or FISH results (as well as FLT3 results) on samples from blood or marrow that were obtained up to 3 weeks before signing consent for purposes of eligibility and stratification. In any case, results from FISH or karyotype should show if CBF abnormalities are present by time of randomization as the presence of CBF abnormalities is a required stratification factor.

3.1.2. Age ≥ 18 and ≤ 75 years.

Because no dosing or AE data are currently available on the use of Pembrolizumab (MK-3475) in patients < 18 years of age, children are excluded from this study, but will be eligible for future pediatric trials.

